***Note on primary outcome time frame**

Our original outreach timeline was to send a letter on the first day of the study, a patient portal message 2 weeks later, an SMS 2 weeks after that (4 weeks after the letter), and measure the primary outcome 2 weeks after the final message. Therefore, we had planned to measure the primary outcome 6 weeks after the study start date, with 2 weeks between the final message and primary outcome measurement.

However, due to administrative and technical delays outside our control, patient portal messages were sent 18 days after the letters, and SMS messages were sent on 3 separate days - 15 days, 24 days, or 25 days after the patient portal messages. Given deviations from

our planned pacing, we changed the primary outcome time frame to 2 weeks following the final outreach date, which is 11/5/21, 8 weeks + 1 day after the study start date.

Corrections for multiple comparisons

For questions 1-3, we provided clear, independent hypotheses above. We will not correct for multiple comparisons in these analyses, as adjustment is not appropriate for individual testing, where each result must be statistically significant to reject its associated individual null hypothesis (Rubin, 2021). That is, each significant result is an indicator of a specific null hypothesis rejection and has no direct bearing on the success of other hypotheses or the overall study.

Because the analysis proposed to address question 4 is exploratory and involves 3 separate pairwise comparisons against the joint null hypothesis that there is no significant difference across the groups, reported p-values will be adjusted for family-wise error rate across the three comparisons using Tukey's HSD.

Sensitivity analyses and robustness checks

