We will also rerun the OLS regression analyses including a binary covariate for whether each patient has an assigned Primary Care Provider (PCP) who works at Geisinger, as flu shot data in the Geisinger EHR may be less reliable from those with an external PCP.

Finally, as an additional robustness check, we will run OLS regression analyses controlling for sex, 10-year age bins, and interactions among sex and age as covariates.

Secondary outcomes

We will use the approaches described in analyses 1-4 above to evaluate the impact of the intervention on the secondary outcome measures listed in the pre-registration:

1. Flu vaccination at 9 weeks after the final outreach date [Time Frame: Within 9 weeks of the final outreach date, within 15 weeks + 1 day of the study start] *

Received a flu vaccination

2. Flu diagnosis [Time Frame: 8 months (between September 9, 2021 and April 30, 2022)]

Received a "high confidence flu" diagnosis (with positive polymerase chain reaction [PCR]/antigen/molecular test) and/or "likely flu" diagnosis (as assessed via International Classification of Disease [ICD] codes or Tamiflu administration or positive PCR/antigen/molecular test)

3. Flu complications [Time Frame: 11 months (between September 9, 2021 and July 31, 2022)]

Diagnosed with flu-related complications

4. Healthcare utilization [Time Frame: 11 months (between September 9, 2021 and July 31, 2022)]

Visited ER, was hospitalized, or had flu-related insurance claims

*Because our outreach timeline was delayed (see above), we will delay the time frame for Secondary Outcome 1 from 3 months following the study start to 9 weeks following the final outreach date.

Additional exploratory analyses

1. Number of reasons

Patients in groups 4 and 5 were randomized to receive either 1 or 3 of the top reasons why they were considered high risk for flu. We will run an OLS regression testing for main effects and interactions between the number of reasons (1 reason, 3 reasons) and message type (group 4: medical records message, group 5: algorithm message) on flu vaccination.

2. Age

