While older patients tend to be aware of their increased vulnerability, younger patients may be more surprised to learn of their high-risk status. We will therefore examine the differential response of patients 65 or above vs. below age 65 by introducing this age variable as a moderator and assessing if it interacts with experimental group to affect vaccination behavior. We will also conduct this analysis using age as a continuous variable.

3. Modality

Patients who received intervention messages (groups 2, 3, 4, and 5) may have received communications via up to 3 modalities. We will employ OLS regression to evaluate the impact of modality on outcomes of interest, assessing pairwise comparisons of the following modality combinations: letter only, letter + myGeisinger, letter + SMS, or letter + myGeisinger + SMS. Note that the number of modalities was not randomly assigned, but determined by patient preferences and data availability in the EHR, so these are observational analyses only.

4. Timing of shot

We will investigate whether the intervention messages influenced the timing (time elapsed since the beginning of the intervention, September 9, 2021) of flu shots. We will do this nonparametrically by graphing the rate at which subjects get a vaccination against time since the intervention began, separately by arm. We will employ regression analyses to test whether timing was differentially affected as well.

5. Timing of SMS

This analysis will focus on the subgroup of patients who were sent SMS messages. As mentioned previously, due to delays outside our control, SMS messages were sent on 3 separate days - 15 days, 24 days, or 25 days after patient portal messages. We will test whether there was a difference in flu shot uptake or timing in those who received earlier messages (15 days following the portal message) compared to those who received later messages (24 or 25 days after the portal message).

To this end, we will run the following analyses: (1) a linear regression testing for effects of message timing (early or late), message type (group 2, 3, 4 or 5), or their interaction, on flu shot uptake, and (2) a flu shot timing analysis, but also testing for main effects of a binary message-timing predictor variable (early or late) and interactions between message type and timing.

Analysis exclusion criteria

The following groups of patients will be excluded from all analyses:

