Contraindicated patients: We unintentionally failed to remove a small number of patients contraindicated for flu vaccines from the sample prior to sending letters. After the error was discovered (after letters were sent, but prior to myGeisinger or SMS messages), because this was an exclusion criterion for the study, we removed the patients completely from the study, including from all analyses.

Patients deceased prior to our study start date (9/9/21): Midway through the study, we received an updated list of patients who were deceased. Some had died prior to the study beginning but medical records had not yet been updated to reflect the date of death. These patients will be removed from all analyses.

The following groups of patients will be excluded from all analyses, except the intent-to-treat analysis (robustness analysis) as described above:

Patients deceased during the study: A very small number of patients were recorded as deceased between the date we originally pulled the data and the date of the updated pull. These patients will be removed from analyses.

Patients sent protective risk reasons: Additionally, in determining the reasons each person was considered high risk, we unintentionally included reasons that were negatively weighted for a small number of patients. That is, for these patients, one or two of the reasons listed for their high-risk determination were *protective* against flu, despite their overall high-risk designation by the model. These patients will be removed because their messages may have been confusing and were not the precise messages we originally intended to send. For consistency across groups, we will also remove those in groups who were not sent reasons, but who would have received protective risk reasons had reasons been included in their messages.

Patients vaccinated prior to the study beginning: Area pharmacies and some Geisinger clinics began offering flu vaccines prior to our study beginning. We will remove patients from analysis who received a flu shot prior to 9/9/21, the study start date.

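### The exploratory SMS-timing regression compares delay-formed batches without a baseline check or an observational label, so an early-late difference cannot be read as an effect of send date

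*SAP*

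**What the plan says.** The SAP's note on the primary outcome time frame reports that "patient portal messages were sent 18 days after the letters" and that "SMS messages were sent on 3 separate days - 15 days, 24 days, or 25 days after the patient portal messages". The primary cut-off was then moved to "2 weeks following the final outreach date, which is 11/5/21, 8 weeks + 1 day after the study start date".

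Under Additional exploratory analyses, item 5 (Timing of SMS) restricts attention to patients who were sent a text. It calls the 15-day batch early and the 24- and 25-day batches late. Two analyses follow: "a linear regression testing for effects of message timing (early or late"), message type (groups 2 to 5) and their interaction on uptake; and a shot-timing analysis with the same early/late predictor. On the origin of the dates, the item says only that "due to delays outside our control, SMS messages were sent on 3 separate days".

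Item 3 (Modality), in the same list, carries a caution: "Note that the number of modalities was not randomly assigned". It concludes that the modality comparisons are observational. Item 5 has no such statement.

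On which shots count, the exclusion criteria say: "We will remove patients from analysis who received a flu shot prior to 9/9/21, the study start date". No later starting point is set for item 5, and no uptake window is named for it.

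**The concern.** The SAP describes randomisation of message group within risk stratum, and of one versus three reasons within groups 4 and 5. It describes none for SMS send date and does not say how a patient came to be in one batch or another. The early-late comparison is therefore between groups formed by operations. The named model has no batch characteristics, no patient covariates and no check that the batches were alike before the first text. The age/sex and Geisinger-PCP robustness checks are set out earlier, for the primary analyses, and are not clearly extended to item 5.

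One documented route by which send date could affect who is in a batch is returned mail. Patients whose letter came back before a modality's send date were not sent that message, so a later batch allowed 9 or 10 more days for such patients to drop out. The SAP describes the untreated fraction as small.

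At stake is the reading of one exploratory result: an operational delay could be reported as evidence on when to text patients.

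**Working it through.** **Dates.** Inputs: start 9/9/21 (exclusion criteria); portal message on day 18; SMS 15, 24 or 25 days later (note on time frame). The plan's own cut-offs reproduce:
- Last SMS: 18 + 25 = day 43 (10/22/21). Adding 14 gives day 57 = 11/5/21 = 8 weeks + 1 day, as stated.
- Secondary cut-off: 43 + 63 = day 106 = 12/24/21, matching "Within 9 weeks of the final outreach date, within 15 weeks + 1 day of the study start".

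| Batch | SMS day | Date | Days to 11/5/21 | Days to 12/24/21 |
|---|---|---|---|---|
| Early | 18 + 15 = 33 | 10/12/21 | 57 − 33 = 24 | 106 − 33 = 73 |
| Late | 18 + 24 = 42 | 10/21/21 | 57 − 42 = 15 | 106 − 42 = 64 |
| Late | 18 + 25 = 43 | 10/22/21 | 57 − 43 = 14 | 106 − 43 = 63 |

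The late batches have 9 or 10 fewer post-SMS days. That is 9/24 = 38% to 10/24 = 42% less at the primary date, and 9/73 = 12% to 10/73 = 14% less at the secondary date. Total follow-up from 9/9/21 is the same for both (57 or 106 days).

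**How a prior difference enters.** Write each batch's uptake as shots before day 33 plus shots from day 33 on, both as a share of the batch. Then

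early − late = (pre_E − pre_L) + (post_E − post_L).

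The first bracket cannot be an SMS effect, because nobody had been texted, yet it passes into the contrast with coefficient 1. Under an assumed constant vaccination hazard reaching 40% by day 57, 74.4% are unvaccinated at day 33. Pre-SMS shots are then 25.6 of 40 points, or 64% of all uptake counted. With 30% or 50% by day 57 the shares are 18.7/30 = 62% and 33.1/50 = 66%. Most of the outcome would thus predate any text. The documents give nothing from which to size pre_E − pre_L.

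**Acceleration versus a lasting difference.** Assume comparable batches and a 2-point SMS effect accruing evenly over A days. Neither assumption is in the SAP. Take 14.5 days as the late average:

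gap at 11/5/21 = 2 × [min(24/A, 1) − min(14.5/A, 1)].
- A = 14: 2 × (1 − 1) = 0
- A = 20: 2 × (1 − 0.725) = 0.55
- A = 24: 2 × (1 − 0.604) = 0.79 (the maximum)
- A = 48: 2 × (0.500 − 0.302) = 0.40

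In all four cases the gap is 0 by 12/24/21, since even 63 days exceeds A. A second illustration assumes that the text raises a constant hazard by 10% to 30% equally in both batches, with 30% to 50% uptake by day 57 without the text. The early batch is then 0.4 to 1.7 points higher at 11/5/21. With no SMS effect the gap is exactly 0.

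**Why a common start date matters.** If uptake were counted from each batch's own SMS date to 11/5/21, the same constant-hazard assumption would give the early batch 5.0 to 9.7 points more with no SMS effect at all. The SAP does not propose this, but any re-analysis must avoid it.

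**The case against.** The strongest reply is that the SAP asks whether earlier and later sending led to different uptake. With uptake counted from 9/9/21 to a fixed date, both batches are followed equally long, and fewer days after a later text is simply what later means. That stands. A reader might infer that the shorter post-SMS time is itself a bias that manufactures a timing effect; the documents do not support this, since with comparable batches and no effective text it produces nothing. What remains is narrower: a gap at 11/5/21 does not show whether the difference lasts.

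It is also fair to say that non-random allocation is inferred. The SAP blames delays and is silent on how batches were made up; if they were effectively random, early-late confounding largely disappears. Pre-SMS shots would then dilute the contrast but not bias it. A reader might go further and infer that the batches did differ. Nothing in the documents shows that.

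Finally, the analysis is filed as exploratory, its own paragraph discloses the delays, and a shot-timing analysis accompanies the uptake regression. All true. None of it supplies a baseline comparison, an adjustment or the caution that the authors gave for modality.

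**Conclusion.** The point holds as a minor one. The planned early-late contrast cannot separate send date from pre-existing batch differences, because allocation is undescribed, no baseline check or adjustment is planned and pre-SMS shots are counted. The size of any confounding is unknown: whatever difference existed before 10/12/21 carries over one for one. The acceleration component is separate and modest, at 0 to 0.8 points for an assumed 2-point SMS effect accruing evenly. The 0.8 is the peak of that model, not an expected value, and the 2 points are borrowed from the trial's two-group design difference, not from any stated SMS increment.

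These conclusions assume that uptake in item 5 is measured at one of the SAP's fixed dates. A reader might infer damage to the main results; there is none, since confirmatory analyses 1a, 1b, 2 and 3 compare randomised groups and do not use SMS send date.

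**What to change.** 1. Label item 5 observational, as for modality, and report how patients were placed in the three SMS batches.
2. Compare early and late batches on vaccination from 9/9/21 up to, but not including, 10/12/21. No text had been sent, so a difference here signals non-comparable batches. Then estimate the early-late uptake contrast among SMS recipients unvaccinated on 10/12/21, using that date as the common start for both batches, adjusted for age, sex, risk stratum (top 3% or next 7%) and Geisinger PCP.
3. Report the contrast at 11/5/21 and again at 12/24/21. A gap that closes by the later date points to acceleration.
4. If a hazard model is used, start it at 9/9/21 with calendar day, a batch term and a time-varying indicator for SMS sent. Days 0 to 32 then inform the batch difference, and days 33 to 41, when only the early batch had been texted, inform the SMS effect. This assumes a batch difference that is stable over time. Starting the model on 10/12/21 without a batch term would repeat the problem, because on days 33 to 41 the SMS indicator is the same thing as early-batch membership.

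The cost is a few lines of SAP text and some extra exploratory work, using vaccination dates that the shot-timing analysis already needs. The SAP states that no outcome data had yet been extracted, so the change could be pre-specified at that point. The downside is a slightly more complex exploratory section and a more cautious conclusion.

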Full Study Protocol

GENERAL INFORMATION

Using AI Risk Predictions to Nudge Flu Vaccination

[name].

[contact]

June 28, 2021

IRB#: 2021-0483

BACKGROUND AND OBJECTIVES

On average, 8% of the US population gets sick from flu each flu season (Tokars et al. 2018). Since 2010, the annual disease burden of influenza has included 9-45 million illnesses, 140,000-810,000 hospitalizations, and 12,000-61,000 deaths (CDC 2020). The CDC recommends the flu vaccination to everyone aged 6+ months, with rare exception; almost anyone can benefit from the vaccine, which can reduce illnesses, missed work, hospitalizations, and death (CDC 2019). Flu vaccination will be especially important for high-risk patients during the COVID-19 pandemic so that flu cases are reduced and resources conserved.

While most recover from influenza without treatment, the elderly, those with comorbidities, and other high-risk individuals can experience complications such as pneumonia, other respiratory illness, and death. Geisinger has partnered with Medial EarlySign (Medial; www.earlysing.com) to develop a machine learning (ML) algorithm to identify patients at risk for serious (moderate to severe) flu-associated complications on the basis of their existing electronic health record (EHR) data. The development of this algorithm was already approved through a separate Geisinger IRB application (**IRB number 2020-0211**). Additionally, Geisinger deployed this system in a field study during the 2020–21 flu season (**IRB number 2020-0290**) and contacted the identified patients with special messages (in addition to standard interventions conducted by the health system every flu season) to encourage vaccination. Geisinger will again deploy this system during the 2021-22 flu season.

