5. High Risk with Explanation Based on Algorithm - message(s) disclosing the patient's *high-risk status* with the added explanation that they are at high risk based on a *computer algorithm review of their medical records* and with the top *reason(s) why they are considered high risk*

Patients in groups 4 and 5 were further randomized to receive one reason or three reasons why they were at high risk (per the medical record review or the algorithm). Randomization occurred separately within each risk and message group. For example, in group 5 (algorithm) half of patients in the top 3% of risk received messages including one reason, while the other half received messages with three reasons.

Message modalities

Patients randomized to groups 2-5 were sent messages in up to 3 modalities: 1. a letter, 2. a myGeisinger (myChart patient portal) message, and 3. an SMS (text) message. Patients with a valid address on file were sent a letter. Patients were sent a myGeisinger message and/or an SMS if they were eligible and if their letter was not returned to sender.

Project status

All intervention messages have been sent. Data collection is ongoing. The study team has not yet extracted or analyzed any outcome data from the study.

Planned Analyses

Primary Outcome

Flu vaccination at 2 weeks after the final outreach date [Time Frame: Within 2 weeks of the final outreach date, 8 weeks + 1 day after the study start] *

Question 1: Does informing patients that they are at high risk for flu and flu-related complications increase the likelihood that they will get vaccinated?

Analysis 1a (Confirmatory): We will test the hypothesis that patients who were sent messages with information about their risk status (patients randomized to message group 3, 4, or 5) will exhibit improved flu vaccination rates compared with patients who were sent messages without risk information (group 2).

Analysis 1b (Confirmatory): We will test the hypothesis that patients who were sent messages with information about their risk status (those in group 3, 4, or 5) will exhibit improved flu vaccination rates compared with patients assigned to the no-contact control group (group 1).

For analyses 1a and 1b, we will run OLS regressions. For both regressions, we will include a binary predictor variable coding separately for baseline (group 2 for analysis 1a and group 1 for analysis 1b), and message (all patients in groups 3-5).

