Some patients lived at the same address, but we decided to randomize patients independently, without accounting for whether a household member was also in the study. Therefore, some patients may have been assigned to different groups from their household members. Alternatively, it is possible household members were assigned to the same group. Either possibility may affect the impact of our intervention (e.g., the same messages received by multiple household members may reinforce the message and strengthen the impact of the messages, while different messages could cause confusion and weaken the messages' effectiveness). To ensure findings do not depend on such interactions between patients residing at the same address, we will run a sensitivity analysis by removing all patients who share an address with another patient in the study and computing the same analyses listed above.

Recent work suggests that OLS regressions are appropriate in randomized experiments with binary outcome variables such as ours (Gomilla, 2021). However, as a robustness check, we will also run the regressions described above as logistic regressions instead of OLS regressions.

Additionally, we plan to exclude some patients from our primary analyses, as noted below in "Analysis exclusion criteria." We will run an intent-to-treat analysis as a robustness check, including all patients who passed away during our study, those who were inadvertently sent protective risk reasons, and those who were vaccinated prior to the study beginning. We will however exclude from all analyses all patients who passed away prior to our study start date (9/9/21), and those inadvertently included despite not satisfying all of the inclusion criteria. A small group of patients did not have a valid mailing address in their medical records, or their print letters were returned to sender. Our subsequent myGeisinger messages referred patients to the letter that was sent. To avoid confusion, we did not send myGeisinger or SMS messages to patients who were never sent a letter, or whose mail was returned prior to these modality send dates. We do not exclude these patients because this would differentially exclude subjects

across the arms. We will note the small fraction of the treatment arms that were not treated for this reason.

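### The main analyses drop patients recorded as deceased between two undated data pulls, a post-randomisation exclusion with no stated reason; its likely effect is small and it is cheap to reverse

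*SAP*

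**What the plan says.** The SAP handles deaths in two groups under Analysis exclusion criteria.

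- **Deaths before 9/9/21** are removed from everything, the intent-to-treat run included. This is where the SAP gives its only timing for the update: "Midway through the study, we received an updated list of patients who were deceased".
- **Deaths during the study** are defined by the data pulls: "A very small number of patients were recorded as deceased between the date we originally pulled the data and the date of the updated pull". This group is "excluded from all analyses, except the intent-to-treat analysis (robustness analysis) as described above". No reason follows. The neighbouring exclusions for contraindication and for protective risk reasons do give one.

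The section Sensitivity analyses and robustness checks refers ahead to those exclusion criteria and then describes the intent-to-treat run as "including all patients who passed away during our study, those who were inadvertently sent protective risk reasons, and those who were vaccinated prior" (that is, before 9/9/21). Here the group is worded by death during the study, without mention of the pulls.

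Under Secondary outcomes, the approaches of analyses 1 to 4 are carried over to later vaccination, flu diagnosis (to 4/30/22), and flu complications and healthcare utilisation (both to 7/31/22). The protocol's background section says that the elderly, those with comorbidities and "other high-risk individuals can experience complications such as pneumonia, other respiratory illness, and death".

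**The concern.** A patient who was randomised, was alive on 9/9/21 and died some weeks later belongs to the randomised comparison. Removing that patient from the main analysis conditions on something that happened after assignment. The exclusion applies to all analyses, so it reaches outcomes to which death is plausibly related: the protocol itself names death among the consequences of influenza in high-risk people. A patient hospitalised with flu in October who then died would contribute neither the diagnosis nor the hospitalisation to the main secondary analyses.

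The SAP reasons differently elsewhere. It keeps patients whose letters could not be delivered because dropping them would affect the arms unequally, and it applies the protective-reason exclusion to arms that received no reasons. The exclusion of deaths comes with no such argument.

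The definition is also loose at its edges. With undated pulls, a death before 9/9/21 that was recorded between the pulls fits the literal wording of this group but belongs to the group removed from everything. The second wording, in the robustness section, does not mention the pulls at all.

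**Working it through.** **1. Dates, counting 9/9/21 as day 0.**

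| Event | Date | Day |
|---|---|---|
| Primary outcome window closes | 11/5/21 | 57 |
| SAP date (updated list already received) | 11/10/21 | 62 |
| Later vaccination outcome (15 weeks + 1 day) | 12/24/21 | 106 |
| Flu diagnosis window closes | 4/30/22 | 233 |
| Complications and utilisation close | 7/31/22 | 325 |

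The SAP reports the updated list as received, so the update came by day 62. Under the definition in the exclusion section, the deaths removed after study start therefore fall within the first 62 days at most. That is at most 62/233 = 27% of the flu-diagnosis window and 62/325 = 19% of the complications and utilisation window. Only events before death in that early stretch are lost.

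**2. The plan's own power figure.** Inputs from the SAP's Power analysis: 9,400 per group, 40% baseline, 2-point difference, 80% power. Alpha is not stated; two-sided 5% is assumed.

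Power = Φ[(0.02 − 1.96·SE₀)/SE₁], with SE₀ = √(2·0.41·0.59/n) and SE₁ = √((0.40·0.60 + 0.42·0.58)/n).

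At n = 9,400: SE₀ = 0.007174, SE₁ = 0.007173, argument 0.828, power 79.6%. The stated 80% reproduces.

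**3. The sample obtained.** 45,164/5 = 9,033 per arm. The argument is 0.773 and power is 78.0%.

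**4. With the deaths removed.** The SAP calls the group very small and gives no count. Assume 0.1% to 0.5%, in equal-sized arms.

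| Share removed | Patients, all arms | Per arm | Power |
|---|---|---|---|
| 0 | 0 | 0 | 78.0% |
| 0.1% | 45 | 9 | 78.0% |
| 0.5% | 226 | 45 | 77.8% |

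**5. Effect on the primary estimate.** Take a 2.00-point difference among retained patients, let f be the share who died, and add the deaths back.

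- *Equal deaths, none vaccinated:* 2.00 × (1 − f) = 1.998 at 0.1% and 1.99 at 0.5%.
- *Deaths 10% lower or higher in the treated arm, none vaccinated:* 0.42(1 − 0.9f) − 0.40(1 − f) and 0.42(1 − 1.1f) − 0.40(1 − f). This gives 2.00 and 1.99 points at 0.1%, and 2.01 and 1.97 at 0.5%.
- *Extreme case, everyone removed vaccinated in one arm and no one in the other:* 2.00(1 − f) ± 100f points. This gives 1.9 to 2.1 at 0.1%, and 1.49 to 2.49 at 0.5%. It is an arithmetic limit, not a plausible scenario.

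**6. Secondary outcomes.** The documents give no event rates for flu diagnosis, complications or utilisation and no death count, so no comparable figure can be worked out.

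**7. The two wordings side by side.** The robustness section excludes no one itself. It defers to the exclusion criteria and lists whom the intent-to-treat run contains. A patient who dies after the updated pull is, under the exclusion section, in the main analysis and so also in the intent-to-treat run. The statement that the run includes everyone who died during the study is then still true.

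**The case against.** The strongest reply is that little is at stake. The group is described as very small, the rule is the same for all arms, and the SAP states: "The study team has not yet extracted or analyzed any outcome data from the study". The intent-to-treat run restores these patients, so both populations are planned and the dispute is largely over which is called main. Most of this stands. It is why the point is minor, and nothing in the documents suggests that deaths differ between arms or that the rule was chosen with results in view.

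Two things remain. The intent-to-treat run brings back deaths together with the protective-reason patients and those vaccinated before the start, so it cannot show what the exclusion of deaths alone does. And a small number is a reason why keeping these patients would cost little, not a reason for removing them.

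A reader might go further and infer that the SAP contradicts itself, with one section excluding deaths only up to the updated pull and the other excluding all deaths to July 2022. The documents do not support that. As step 7 shows, the sections can be read together. The only mortality update described is the one already received, and the protocol's Data Sources section does not name death or date of death among the outcome data, though that list may not be exhaustive. The wording should be aligned, but this is a matter of clarity.

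**Conclusion.** The point holds as a minor one. The main analyses of every outcome exclude patients on an event after randomisation, without a stated reason and between undated pulls, when keeping them would be simple.

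For the primary outcome the effect is negligible: at most about 0.2 percentage points of power, if 0.1% to 0.5% are removed, and a change of a few hundredths of a point in a 2-point difference unless deaths and vaccination status are distributed in an extreme way. Both statements rest on the assumed share.

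For flu diagnosis, complications and utilisation the effect is probably small, because the group is called very small and its post-start deaths fall by day 62 at the latest. It is not quantified. A reader might infer that the trial's results are biased in a particular direction; the documents show no direction and no imbalance in deaths.

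**What to change.** - In the main analysis of every outcome, keep all otherwise eligible patients who were alive on 9/9/21, counting vaccinations, diagnoses, complications and utilisation recorded up to death.
- Make exclusion of deaths a robustness check on its own, so that its effect can be seen separately.
- Define the group by date of death, in the same words, in both Analysis exclusion criteria and Sensitivity analyses and robustness checks. State the dates of the two pulls.
- Report known deaths by arm from the list already received.
- This point requires no change to the exclusions for vaccination before the start or for protective risk reasons.

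The cost is SAP wording and at most one extra run. At the SAP's date, with no outcome data yet extracted, the change could have been made without knowledge of results. Reporting deaths after the updated pull would need a later mortality extract, which the documents do not describe.
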